#### **GCP Statement**

This study is to be performed in full compliance with the protocol, Good Clinical Practices (GCP), and applicable regulatory requirements. All required study documentation will be archived as required by regulatory authorities.

## 1. PROTOCOL REVISION HISTORY

DATE/NAME	DESCRIPTION
14May2018 by [name]	
Final Protocol, Amendment 2:
 
Following on FDA recommendations, the following changes were made to the protocol:
 

1. The dosing interval between the sentinel group and the remaining subjects was revised to at least 28 days in Cohort 1 and 14 days in the remaining cohorts. The protocol was updated throughout to reflect this change.

2. The following study stopping rules were added to bullet number 5 in Section 10.4.1.4 Dose Escalation and Stopping Rules:

I. <math>\geq 1</math> subject that receive drug in a cohort experience:

a. Life-threatening hypersensitivity reactions (e.g., anaphylaxis, respiratory symptoms, hypotension etc.).

b. Any grade thromboembolic event possibly related to the study drug.

c. Any grade bleeding possibly related to the study drug.

d. Presence of antibodies against human thrombin or prothrombin.

e. Presence of ADA.

DATE/NAME	DESCRIPTION
	
4. If aPTT and/or thrombin time values do not reach <math>\pm 10\%</math> of the baseline value or within the normal range by Day 14, sampling will continue every 7 days (<math>\pm 2</math> days) until the <math>\pm 10\%</math> of baseline value or the normal range is reached. Subjects will return for a FU visit (i.e., follow-up procedures and AE evaluation listed on Day 28 will be repeated) 7 days (<math>\pm 2</math> days) after aPTT and thrombin time values reach <math>\pm 10\%</math> of the baseline value or within the normal range. The protocol was updated throughout to reflect this change.
 
5. To be consistent with the Coagulation panel, “Fibrinogen” was added to the list in the Coagulation row in Section 6 Study Event Flow Chart.
 
In addition, the following updates were made:
 
6. The last sentence of the 4th paragraph in Section 10.4.3 Method of Assigning Subjects to Treatment Groups, was corrected for consistency throughout the protocol to read (added text in bold and deleted text in <del>strickthrough</del>):
 
<del>For Cohorts 2-4, t</del>The placebo will be randomized to either group.
 
7. The name of the IRB was changed from Chesapeake IRB to Advarra. Section 13.1.1 Institutional Review Board was updated.
 
8. Typographical and formating edits were performed throughout the protocol.

27Mar2018 by [name]
	
Final Protocol, Amendment 1:
 
This protocol was amended to correct a mathematical discrepancy in the total blood volume being drawn in this study.
 
In Section 11.4 – Table 3: the frequency of blood draws and individual blood draw volumes were correct however, the total blood volumes (number of timepoints multiplied by volume drawn) was incorrect for the following rows:
 
 
1) “On-study coagulation (aPTT, PT/INR, fibrinogen, and, if scheduled at the same time, thrombin time)”, the volume was decreased from 38.5 to 35 mL.
 
2) “Blood for APC-PCI (Celerion)”, the volume was increased from 24 mL to 32 mL.
 
3) Therefore the sum of all blood volumes, indicated in the rwo “Total Blood Volumes” was increased from 177.8 mL
 

DATE/NAME	DESCRIPTION
	to 182.3 mL. In addition to the change above the reference list was updated to remove an extraneous reference Chow et al., 1992 and Gough K., et al., 1995.
19Feb2017 by [name]	Final

## 5. SYNOPSIS

Compound	
E-WE thrombin
 
Active ingredient: E-WE thrombin (0.1 mg/mL) Buffer: 16.2 mM sodium citrate, 3.8 mM citric acid, 150 mM sodium chloride, 0.1% polysorbate 80, at pH 6

Clinical Indication	Prevention and treatment of arterial thrombosis and thromboembolism
Study Phase and Type	Phase 1, single ascending dose (SAD) study, first-in-human study
Study Objectives	
The primary objective of the study is to assess the safety and tolerability of single intravenous (IV) bolus doses of E-WE thrombin when administered to healthy adult subjects.
 
The secondary objective is to assess the pharmacodynamics (PD) of single IV bolus doses of E-WE thrombin when administered to healthy adult subjects. The activated protein C/protein C inhibitor complex (APC-PCI) will be used as a surrogate biomarker for drug exposure.

Study Design	
This is a randomized, double-blind, placebo-controlled, SAD study conducted at one study center in the United States (US).
 
Four (4) cohorts of either 6 subjects (Cohort 1 [4 active and 2 placebo]) or 5 subjects (Cohorts 2, 3, and 4 [4 active and 1 placebo]) are planned for evaluation. In each cohort, subjects will receive a single IV bolus of E-WE thrombin or placebo. Subjects will participate in only 1 cohort.
 
Two (2) sentinel subjects will be dosed (1 placebo and 1 active) in Cohort 1 and data will be collected through Day 28. The remaining subjects in the cohort will be dosed after evaluation of the sentinel subjects' Day 28 safety data and will be dosed in 2 groups separated by at least 14 days (2 subjects in the first group and 2 subjects in the second group). The placebo will be randomized to either group.
 
The Cohorts 2, 3, and 4 will be dosed in 2 groups separated by at least 14 days (2 subjects in the first group and 3 subjects in the second group). The placebo will be randomized to either group.
 
Safety (i.e., physical examinations, vital signs, electrocardiograms (ECGs), clinical laboratory tests [including coagulation], thrombin time, immunogenicity, injection site reaction, and adverse events [AEs]) will be assessed throughout the study.

	
Blood samples will be collected for PD assessment (i.e., APC-PCI) of E-WE thrombin at scheduled time points listed in the Study Events Flow Chart (Section 6) predose and for 24 hours postdose.
 
Dose escalation to the next dose level (i.e., next cohort) will not take place until after the Principal Investigator (PI) has reviewed the safety data and informed the Sponsor of the findings. If any findings in the safety data are of concern, then the Safety Review Committee (SRC) comprised of but not limited to, the Sponsor, medical monitor, and the PI will convene to determine if adequate safety and tolerability from the previous cohorts, including activated partial thromboplastin time (aPTT), has been demonstrated to permit proceeding to the next cohort.
 
For each cohort, 14 days of safety data will be used and reviewed for a dose escalation decision. Data from all subjects in the appropriate cohort will be used and reviewed for a dose escalation decision. aPTT and thrombin time should be in the normal range (unless it is still within <math>\pm 10\%</math> of individual's baseline value taken at check-in) at Day 14 to rule out early cross-reacting antibodies to thrombin/prothrombin. A minimum of 4 subjects in each cohort must complete the study (up to Day 14) before proceeding to the next higher dosing cohort.
 
Subjects dosed on the same day will be dosed with an interval of at least 1 hour between subjects.
 
Subjects (including those who terminate early) will return on Days 14 and 28 for follow-up procedures (coagulation sample collection, thrombin time measurement, and immunogenicity sample collection) and to determine if any AE has occurred since the last study visit. If thrombin time and/or aPTT are found to be elevated beyond normal range (unless it is still within <math>\pm 10\%</math> of individual's baseline value at check-in) at Day 14, both tests will be repeated. If aPTT and/or thrombin time are elevated beyond normal range in the retest, a mixing study will be performed. The mixing study will be performed on Day 14 by mixing the subjects' plasma 1:1 with normal human pooled plasma. aPTT and thrombin time will be evaluated. If the aPTT and/or thrombin time does not correct to normal range, the presence of anti-drug antibodies (ADA) and cross-reacting prothrombin/thrombin antibodies will be presumed, and will be directly assessed before dose escalation decision.
 
Subjects who terminate the study early will be asked to continue aPTT and thrombin time monitoring as scheduled until Day 28.
 
Any subjects for whom aPTT and/or thrombin time did not reach

--	--

	
± 10% of the baseline value or within the normal range by Day 14, will return every 7 days (±2 days) until aPTT and thrombin time reach ±10% of the baseline value or within the normal range and for a FU visit (i.e., follow-up procedures and AE evaluation listed on Day 28 will be repeated) 7 days (± 2 days) after it was reached.

Study Population	
Subjects will be healthy male subjects and healthy female subjects of non-childbearing potential.

Number of Subjects	
The study is planned to enroll up to 21 subjects in 4 cohorts [i.e., dose levels] with 6 subjects in Cohort 1 [4 subjects randomized to receive the active drug and 2 subjects to receive the placebo] and 5 subjects in Cohort 2, 3, and 4 [4 subjects randomized to receive the active drug and 1 subject to receive the placebo].
 
In each cohort, an attempt will be made to have at least 30% of the subjects be of a race/ethnicity minority group. An attempt will be made to include at least 2 females in each cohort.
 
Additional subjects (up to 6 subjects per cohort) may be enrolled if it is deemed appropriate by the PI and the Sponsor to repeat a dose level or to study an intermediate dose level (lower than those planned) in a new cohort of subjects.

Duration of Participation for Subjects	
The total planned duration of subject participation is approximately 56 days from screening to last visit, with clinical research unit (CRU) confinement from check-in on Day -1 to Day 2. Subjects will return to the CRU on Day 14 and Day 28 for follow-up procedures.

Study Products	
E-WE thrombin will be supplied as sterile, non-pyrogenic, preservative-free liquid for IV administration.
 
E-WE thrombin will be supplied as 0.1 mg/mL for IV use and given as a single IV bolus, according to the planned dose (mcg/kg) for each cohort, as noted below.
 
Matching placebo will be supplied as sterile formulation buffer for injection via IV route.
 
An unblinded pharmacist will be responsible for providing E-WE thrombin or placebo to the blinded study personnel for IV bolus administration.

Planned Dose Levels	
On Day 1, subjects in each cohort will receive an IV bolus over 15 seconds up to 1 minute of E-WE thrombin or matching placebo on one occasion.
 
Planned doses will be as follows:

	
Cohort 1: 0.5 mcg/kg E-WE thrombin or matching placebo Cohort 2: 1.0 mcg/kg E-WE thrombin or matching placebo Cohort 3: 2.0 mcg/kg E-WE thrombin or matching placebo Cohort 4: 4.0 mcg/kg E-WE thrombin or matching placebo Dosing will not exceed 4.0 mcg/kg without a protocol amendment.

Safety Assessments	
Safety will be monitored through vital signs, ECGs, clinical laboratory tests (including, but not limited to, hematology, serum chemistry profile, coagulation, and urinalysis), immunogenicity, injection site reaction, and AEs.

Safety Analysis	
No formal inferential statistics will be done on safety assessments.
 
The placebo subjects from all cohorts will be pooled into a single placebo group for all summaries and presentations.
 
Descriptive statistics will be calculated for quantitative safety data and frequency counts will be compiled for classification of qualitative safety data, as appropriate.
 
Adverse Events: AEs will be coded using the most current version of Medical Dictionary for Regulatory Activities® (MedDRA®) available at Celerion.
 
A by-subject AE data listing, including verbatim term, preferred term, treatment, severity, and relationship to drug, will be provided.
 
The number of subjects experiencing treatment-emergent adverse events (TEAEs) and number of TEAEs will be summarized by treatment using frequency counts.
 
Injection site reaction will be assessed.
 
Medical History and Physical Examination: Medical history will be listed by subject.
 
Changes in physical examinations will be described in the text of the final report.
 
Clinical Laboratory Results, Electrocardiograms, and Vital Signs Measurements: All clinical laboratory results (including coagulation), 12-lead ECGs, vital signs measurements, and their change from baseline, will be summarized by dose level and time point of collection.
 
A shift table describing out-of-normal range shifts will be

	
provided for clinical laboratory results. Thrombin time will be assessed.
 
Concomitant Medications: Concomitant medications will be listed by subject.
 
Immunogenicity: ADA detection will be reported and summarized descriptively.

Pharmacodynamic Sample Collection	
Serial blood samples will be collected prior to and for 24 hours following the dose on Day 1 to determine APC-PCI levels, which will be performed by Celerion. The Sponsor will assess the real-time aPTT on-site, and also evaluate protein C.
 
The sampling schedule may be modified based on the results from previous cohorts.

Pharmacodynamic Analysis	
APC-PCI values will be listed and presented graphically.

## 6. STUDY EVENTS FLOW CHART

Study Procedures a	Days → Hours →	Scr b	Study Days in Each Cohort c										FU d			
			-1	1									2 e	14	28	
			C-I f	P	0	0.083	0.25	0.5	1	2	4	24				
Administrative Procedures																
Informed Consent		x														
Inclusion/Exclusion Criteria		x	x													
Medical History		x														
Safety Evaluations																
Full Physical Examination g		x														
Injection Site Assessments				x					x				x			
Height		x														
Weight		x	x													
Vital Signs (heart rate, blood pressure, respiratory rate and temperature)		x		x h			x	x	x	x	x	x				
Safety 12-Lead Electrocardiogram		x		x h								x				
Hem, Serum Chem i , and UA		x	x									x				
Coagulation (Fibrinogen, aPTT j , and PT/INR)		x		x		x	x	x	x	x	x	x	x	x		
Thrombin Time j			x											x	x	
Serum Pregnancy Test (females only)		x	x													
Serum FSH (postmenopausal females only)		x														
Urine Alcohol and Drug Screen		x	x													
HIV/Hepatitis Screen		x														
AE Monitoring																
Concomitant Medication Monitoring		x														
Study Drug Administration / Pharmacodynamics																
E-WE Thrombin Administration k					x											
Blood for PD: Plasma for APC-PCI				x		x	x	x	x	x	x	x				

Study Procedures a	Scr b	Study Days in Each Cohort c										FU d	
		-1	1									2 e	14
Days →		C-I f	P	0	0.083	0.25	0.5	1	2	4	24		
Hours →													
Other Procedures													
Plasma and Serum Immunogenicity l		x										x	x
Blood for protein C (Aronora)			x					x	x		x		
Blood for Real-Time aPTT (Aronora)			x		x	x	x	x	x	x	x		
Confinement in the CRU		x											
Visit and Return Visits	x											x	x

- a For details on Procedures, refer to [Section 11](#).
- b Within 28 days prior to study drug administration.
- c Cohort 1 will include a sentinel group of 2 subjects randomized in a 1:1 ratio for active to placebo who will be dosed at least 28 days before the remaining subjects. The remaining subjects in Cohort 1 will be dosed in two groups separated by at least 14 days (2 subjects in the first group and 2 subjects in the second group). The Cohorts 2, 3, and 4 will be dosed in two groups separated by at least 14 days (2 subjects in the first group and 3 subjects in the second group). The placebo will be randomized to either group.
- d Subjects (including those who terminate early) will return on Days 14 and 28 for follow-up procedures (coagulation sample collection, thrombin time measurement, and immunogenicity sample collection) and to determine if any AE has occurred since the last study visit. Subjects who terminate the study early will be asked to continue aPTT and thrombin time monitoring as scheduled until Day 28.  
Any subjects for whom aPTT and/or thrombin time did not reach  $\pm 10\%$  of the baseline value or within the normal range by Day 14, will return every 7 days ( $\pm 2$  days) until aPTT and thrombin time reach  $\pm 10\%$  of the baseline value or within the normal range and for a FU visit (i.e., follow-up procedures and AE evaluation listed on Day 28 will be repeated) 7 days ( $\pm 2$  days) after it was reached.
- e To be performed prior to discharge from the CRU or prior to early termination from the study.
- f Subjects will be admitted to the CRU on Day -1, at the time indicated by the CRU.
- g Full physical examination will be performed at screening. A symptom-driven physical examination may be performed at other scheduled times, at the PI's or designee's discretion.
- h To be performed within 24 hours prior to dosing.
- i Samples for serum chemistry will be obtained following a fast of at least 8 hours, however, in case of dropouts or rechecks, subjects may not have fasted for 8 hours before the serum chemistry sample is taken.
- j If thrombin time and/or aPTT are found to be elevated at Day 14, both tests will be repeated. If aPTT and/or thrombin time are elevated beyond the normal range (unless it is still within  $\pm 10\%$  of individual's baseline value at check-in) in the retest, a mixing study will be performed. The mixing study will be performed on Day 14 by mixing the subjects' plasma 1:1 with normal human pooled plasma. aPTT and thrombin time will be evaluated. If the aPTT and/or thrombin time do not correct to normal range, the presence of ADA cross-reacting prothrombin/thrombin antibodies will be presumed. The applicable subject will remain at the CRU until

these test results are obtained. Subjects for whom aPTT and/or thrombin time did not reach  $\pm 10\%$  of the baseline value or within the normal range by Day 14, will return every 7 days ( $\pm 2$  days) until aPTT and thrombin time reach  $\pm 10\%$  of the baseline value or within the normal range.

- k Subjects in the sentinel group (Cohort 1 only) will be dosed at least 28 days prior to remaining subjects. The remaining subjects in Cohort 1 and subjects in the Cohorts 2, 3, and 4 will be dosed in two groups separated by at least 14 days. Dosing in each group will be staggered by at least 1 hour.
- l: Immunogenicity testing for ADA will be first performed on blood samples taken on Days 14 and 28. If ADA are found, the check-in sample of ADA will be evaluated.

Abbreviations: ADA = Anti-drug antibodies, AE = Adverse event, APC-PCI = Activated protein C with protein C inhibitor, aPTT = Activated partial thromboplastin time, C-I = Check-in, Chem = Chemistry, CRU = Clinical research unit, FSH = Follicle-stimulating hormone, FU = Follow-up, Hem = Hematology, HIV = Human immunodeficiency virus, INR = International normalized ratio, PD = Pharmacodynamic, PI = Principal Investigator, PT = Prothrombin time, Scr = Screening, UA = Urinalysis.

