### **8.2.4 Pharmacodynamics**

Injection of E-WE thrombin results in the temporal and selective generation of endogenous APC, and escape of some APC from the surface into the blood circulation. In the circulation, APC inactivates factor Va and factor VIIIa, resulting in a temporal prolongation of the aPTT. The activity of APC is regulated in part through its enzymatic interactions with serine protease inhibitors to form inactive enzyme inhibitor complexes, primarily APC-PCI and APC-antitrypsin complexes. The half-life of exogenous recombinant APC is 15 to 25 minutes in blood, and data from baboons suggest that the half-life of endogenous APC is comparable. The rate of APC inhibition by PCI in plasma is significantly accelerated in the presence of heparin, and the APC-PCI complex is reported to have a half-life of 20 minutes in the circulation.

In preclinical Study Report No. AB002.4, the APC-PCI complex was evaluated as a biomarker for E-WE thrombin activity in a baboon. The systemic effect of an IV bolus of E-WE thrombin (0.75 to 10 mcg/kg) on APC-PCI complex formation and corresponding aPTT was evaluated over 2 hours. Injection of E-WE thrombin caused a dose-dependent increase in APC-PCI plasma levels. Elevated levels of APC-PCI were present between 5 and 120 minutes post administration at all four dose levels, with peak APC-PCI levels observed approximately 30 minutes after E-WE thrombin injection. By 120 minutes post injection, APC-PCI values were trending toward baseline.

In the same baboon, aPTT prolongation was also evaluated. E-WE thrombin caused a dose-dependent transient increase in the aPTT at all four dose levels, peaking at approximately 15 to 30 minutes post administration, with peak prolongation ranging from approximately 1.2-fold to 1.8-fold over baseline value. aPTT returned to baseline by 120 minutes at all doses tested except the highest dose. The duration and magnitude of the aPTT elevation in response to E-WE thrombin correlated with plasma APC-PCI concentrations and the fold increase in aPTT prolongation significantly correlated with APC-PCI concentration:

( $R^2 = 0.85$ ,  $p \leq 0.001$  by linear regression).

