### **10.2.4 Follow-up Visits (Day 14 and 28)**

Subjects (including those who terminate early) will return on Days 14 and 28 for follow-up procedures (coagulation sample collection, thrombin time measurement, and immunogenicity sample collection) and to determine if any AE has occurred since the last study visit. If thrombin time and/or aPTT are found to be elevated beyond normal range (unless it is still within  $\pm 10\%$  of individual's baseline value at check-in) at Day 14, both tests will be repeated. If aPTT and/or thrombin time are elevated beyond the normal range in the retest, a mixing study will be performed. The mixing study will be performed on Day 14 by mixing the subjects' plasma 1:1 with normal human pooled plasma and thrombin time evaluated. If the thrombin time does not correct, the presence of ADA and cross-reacting prothrombin/thrombin antibodies will be presumed and will be directly assessed before dose escalation decision. The applicable subject will remain at the CRU until these test results are obtained.

Subjects who terminate the study early will be asked to continue aPTT and thrombin time monitoring as scheduled until Day 28.

Any subjects for whom aPTT and/or thrombin time did not reach  $\pm 10\%$  of the baseline value or within the normal range by Day 14, will return every 7 days ( $\pm 2$  days) until aPTT and thrombin time reach  $\pm 10\%$  of the baseline value or within the normal range and for a FU visit (i.e., follow-up procedures and AE evaluation listed on Day 28 will be repeated) 7 days ( $\pm 2$  days) after it was reached.

Should any subjects withdraw or be withdrawn from the study, all the early termination evaluations should be performed if possible, including samples for PD assessments if applicable.

Immunogenicity samples will be collected at the follow-up visits. The follow-up procedures are listed in the Study Events Flow Chart [Section 6](#).

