### 10.3.4 Early Termination of Subjects from the Study

Subject participation in this trial may be discontinued for any of the following reasons:

1. Occurrence of any medical condition or circumstance that exposes the subject to substantial risk and/or does not allow the subject to adhere to the requirements of the protocol.
2. Any SAE, clinically significant AE, severe laboratory abnormality, intercurrent illness, or other medical condition that indicates to the PI or designee that continued participation is not in the best interest of the subject.
3. Subject's decision to withdraw.
4. Requirement of prohibited concomitant medication.
5. Subject failure to comply with protocol requirements or study related procedures.
6. Termination of the study by the Sponsor, FDA, Celerion, or other regulatory authorities.
7. Pregnancy.

The clinical report will include reason(s) for subject withdrawals as well as details relevant to the subject withdrawal. If a subject is withdrawn from the trial prior to study completion, the subject will undergo all procedures scheduled for subjects who terminate early (see [Section 6](#)) as the situation allows (see [Section 10.2.4](#)). Any subject withdrawn due to an AE (whether serious or non-serious) or clinically significant abnormal laboratory test values will be evaluated by the PI or designee or a monitoring physician and will be treated and/or followed up until the symptoms or values return to normal or acceptable levels, as judged by the PI or designee.

Subjects withdrawn may be replaced at the Sponsor's discretion.

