## 11.4 Blood Volume for Study Assessments

**Table 3: Blood Volume during the Study**

Sample Type	Number of Time Points	Approximate Volume per Time Point * (mL)	Approximate Sample Volume Over Course of Study (mL)
Screening laboratory safety tests (including hematology, serum chemistry, serology, and coagulation), FSH (for postmenopausal female subjects only) and serum pregnancy (for female subjects only).	1	16	16
On-study hematology, serum chemistry (this includes serum pregnancy for female subjects only when scheduled at the same time)	2	12.5	25
On-study coagulation (aPTT, PT/INR, fibrinogen, and, if scheduled at the same time, thrombin time)**	10	3.5	35
Thrombin Time only	1	3.5	3.5
Blood for plasma immunogenicity (E-WE thrombin plasma ADA) (Celerion)	3	9	27
Blood for serum immunogenicity (WT thrombin serum ADA) (Celerion)	3	5	15
Real-time aPTT: Citrated (3.2%) blood for aPTT (Aronora)	8	2.7	21.6
Real-time protein C: Citrated (3.2%) blood for protein C (Aronora)	4	1.8	7.2
Blood for APC-PCI (Celerion)	8	4	32
Total Blood Volume (mL)→			182.3***

\* Represents the largest collection tube that may be used for this (a smaller tube may be used).

\*\* If by Day 14 aPTT and/or thrombin time values have not returned within  $\pm 10\%$  of the baseline value or the normal range, sampling will continue every 7 days ( $\pm 2$  days) until the  $\pm 10\%$  of baseline value or to the normal range is reached or a maximum of ~500 mL of blood is collected from the subject. Subjects who terminate the study early will also be asked to return every 7 days ( $\pm 2$  days) for aPTT and thrombin time monitoring until values return within  $\pm 10\%$  of baseline value or the normal range.

\*\*\* If additional safety or PD analysis is necessary or if larger collection tubes are required to obtain sufficient plasma/serum for analysis, additional blood may be obtained (up to a maximum of 50 mL).

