**Table 8.1 Laboratory Data Time Points**

Test	Period	Day	Hour
Serum Chemistry/ Hematology/ Urinalysis	Screen		
	1	-1	Check-in
		2*	24
Coagulation	Screen		
		1	Predose, 0.083, 0.25, 0.5, 1, 2, 4
		2*	24
		14	FU
		28	FU
*Prior to discharge from CRU or at early termination from the study. FU = Follow-up			

Out-of-normal range flags (1st flag) will be recorded as follows:

- for numerical results: high (H) and low (L);
- for categorical results: did-not-match (\*).

If a value fails the reference range, it will automatically be compared to a computer clinically significant (CS) range (2nd flag).

- If the value falls within the computer CS range, it will be noted as “N” for not clinically significant.
- If the value fails the CS range, it will be flagged with a “Y” which prompts the PI to determine how the out-of-range value should be followed using 4 PI flags (3rd flag):
  - "N", not clinically significant,
  - "R", requesting a recheck,
  - "^", checking at the next scheduled visit,
  - "Y", clinically significant.

To distinguish the PI flags from the computer CS range flags, the PI flags “N” and “Y” will be presented as “-“ and “+” in the data listing, respectively.

In addition, a derived flag (a 4th flag) based on a search of the PI comments for a comment of “CS” or “Clinically Significant” will be used. The derived flag will be populated with “+” if the positive clinically significant determination is found in the comments for cases when the PI flag is populated with a “^” or a “R”.

Out-of-range values and corresponding recheck results will be listed. Out-of-range values are considered to be values that are out-of- normal range as defined by the clinical laboratory. Results that are indicated as CS by the PI (either in the PI flag or in PI comments) will be also listed in a separate table.

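### The early-termination battery has no thrombin time or antibody sample, which matters for a subject who attends an exit visit after Day 2 and does not return

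*Protocol*

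**What the plan says.** Protocol Section 10.3.4 states that on withdrawal "the subject will undergo all procedures scheduled for subjects who terminate early", circumstances permitting, and refers to Sections 6 and 10.2.4. Neither defines a separate exit battery. Section 6 offers footnote e, attached to the Day 2 (24-hour) column: "To be performed prior to discharge from the CRU or prior to early termination from the study". SAP Table 8.1 marks Day 2 in the same way ("Prior to discharge from CRU or at early termination from the study"), as do the SAP tables for vital signs, ECG and injection site. Section 10.2.4 adds that "all the early termination evaluations should be performed if possible, including samples for PD assessments if applicable".

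The flow-chart rows for thrombin time and "Plasma and Serum Immunogenicity" are marked at check-in, Day 14 and Day 28 only. SAP Section 7 gives the same three immunogenicity days.

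Footnote d and Section 10.2.4 ask subjects, early terminators included, to come back on Days 14 and 28 for coagulation, thrombin time and immunogenicity. The follow-on sentence about early terminators mentions only aPTT and thrombin time.

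Under Section 10.4.1.4, criteria I.d and I.e, antibody to human thrombin or prothrombin, or ADA, in one active subject in a cohort ends the study. Under footnote l, the check-in antibody sample is tested only if a Day 14 or Day 28 sample is positive.

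**The concern.** Antibody formation is a one-subject stopping criterion, with only four active subjects per dose level. For someone who leaves and does not return, the exit visit is the last chance to sample. Blood is already drawn there for coagulation, yet the defined battery takes neither the antibody sample nor thrombin time, which is one of the two tests in the indirect antibody screen. Because the check-in sample is tested only after a later positive, a subject lost before Day 14 has no antibody result of any kind.

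Reporting adds to this. In the shell for SAP Table 14.2.2.1, a subject not positive at least once postdose goes into the Overall column as negative, and N is the number dosed. A subject never sampled after dosing would therefore appear as ADA-negative.

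**Working it through.** **1. The plan's own sampling counts (Protocol Table 3).** The row "On-study coagulation (aPTT, PT/INR, fibrinogen, and, if scheduled at the same time, thrombin time" has 10 time points: predose, 0.083, 0.25, 0.5, 1, 2, 4 and 24 h, Day 14 and Day 28. The row "Thrombin Time only" has 1 (check-in). Each immunogenicity row has 3. Total volume: 16 + 25 + 35 + 3.5 + 27 + 15 + 21.6 + 7.2 + 32 = 182.3 mL, as stated. The counts agree with the flow chart, and no thrombin-time or immunogenicity draw falls on Day 2.

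**2. What is available for a subject who attends an exit visit and does not return.**

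| Leaves | Postdose antibody result | Postdose thrombin time | aPTT at exit |
|---|---|---|---|
| After Day 2, before Day 14 | none | none | yes |
| After Day 14 visit, before Day 28 | Day 14 only | Day 14 only | yes |

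**3. Size for the one-subject rule.** With n active subjects assessed and true antibody rate p, the chance of at least one positive is 1 − (1 − p)^n. With no positives, the one-sided 95% upper bound on p is 1 − 0.05^(1/n). The documents give no antibody rate, so the values of p are assumptions.

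| Active subjects assessed | p = 10% | p = 20% | p = 30% | Upper bound if none positive |
|---|---|---|---|---|
| 4 | 0.34 | 0.59 | 0.76 | 53% |
| 3 | 0.27 | 0.49 | 0.66 | 63% |
| 2 | 0.19 | 0.36 | 0.51 | 78% |

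The four-completer minimum in Section 10.4.1.4 is not specified by arm. It would be met with 3 active subjects assessed in Cohorts 2 to 4 (5 − 1 = 4, the one lost being active), or 2 in Cohort 1 (6 − 2 = 4, both lost being active). Section 10.4.1.2 describes the review as covering the full cohort, so these are the lowest numbers the minimum allows, not the expected case.

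**4. Effect of the SAP Overall rule.** Suppose 4 active subjects are dosed, 3 are sampled and negative, and 1 is never sampled. The shell reports 4 of 4 negative, which supports a bound of 53%. The data are 3 of 3 negative, with a bound of 63%.

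**5. Blood volume of the addition.** Thrombin time shares the 3.5 mL coagulation tube, so it adds 0 mL. Immunogenicity adds 9 + 5 = 14 mL. On top of every planned draw the total is 182.3 + 14 = 196.3 mL. A subject leaving before Day 14 also misses two follow-up draws of 3.5 + 14 = 17.5 mL each, 35 mL in all. An exit visit of 12.5 + 3.5 + 14 = 30 mL then gives 182.3 − 35 + 30 = 177.3 mL, without PD tubes.

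**The case against.** The strongest answer is that the planned path already collects these data. Early terminators are asked back on Days 14 and 28 for exactly these tests, whatever their reason for leaving. Nothing in Section 10.3.4 says that a subject who decides to withdraw also refuses follow-up. This stands, and it confines the point to non-returners, whose frequency the documents do not give. Withdrawn subjects may also be replaced at the sponsor's discretion, and the investigator may order unscheduled tests.

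A reader might infer that anyone leaving after Day 2 contributes nothing on the antibody criteria. The documents do not support that: a Day 20 leaver should already have the Day 14 samples, and even a Day 10 leaver has aPTT at exit.

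A reader might also infer that the plan spends late exit blood on PD markers that can no longer be informative, so that exchanging tubes costs only 14 − (4 + 2.7 + 1.8) = 5.5 mL. That is not established. Section 10.2.4 takes PD samples only where applicable, and PD sampling is planned through 24 hours postdose, so there may be no PD tubes to give up. The statement that "the APC-PCI complex is reported to have a half-life of 20 minutes in the circulation" concerns APC-PCI alone; no half-life is given for protein C.

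Finally, the synopsis uses Day 14 to rule out early cross-reacting antibodies, so a negative exit sample before then cannot replace it. Section 11.1.7.1 also ships samples at study end unless thrombin time is raised at Day 14 or 28, so amending footnote e alone would not bring an exit result into any decision. Both points stand and shape the fix.

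On the SAP, the shells are described as layouts that may change. The Overall rule is nonetheless the only rule given for an unsampled subject.

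**Conclusion.** The point holds in a limited form, as a cheap improvement to the plan. The early-termination battery has no thrombin time and no immunogenicity sample. For a subject who attends an exit visit after Day 2 and does not return, this means no postdose antibody or thrombin-time result if the exit is before Day 14, and loss of the later sample if it is between Days 14 and 28.

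The loss is up to 1 of 4 active subjects (25%) at a dose level per such dropout, assuming that the subject was on active drug, left before Day 14 and was not replaced. The table in step 3 shows what is at risk, not what the fix recovers: an exit sample before Day 14 gives partial information, and one taken soon after Day 2 gives little. The SAP rule that turns an unsampled subject into a negative needs correcting whether or not the exit sample is added.

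One inconsistency should be settled at the same time. Protocol Section 11.1.4 lists thrombin time within the coagulation panel, which could be read as a Day 2 and exit draw. The flow chart and the Table 3 row wording contradict that reading.

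**What to change.** **Protocol.**
- Footnote e and Section 10.2.4: for an exit visit after Day 2, add thrombin time (same 3.5 mL coagulation tube) and the plasma and serum immunogenicity samples (14 mL). Keep the request to return on Days 14 and 28, and name immunogenicity in the sentence on continued monitoring of early terminators.
- State that PD samples at early termination apply only within the 24-hour PD sampling window.
- Footnote l and Section 11.1.7.1: cover the exit sample, so that it is assayed and its shipping is defined. Say whether the footnote j retest and mixing steps apply to an exit value; that choice is for the clinical team.
- Reconcile Section 11.1.4 with the flow chart and Table 3 on thrombin time.

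**SAP.**
- Section 7 and the listings: list the exit antibody result at its actual study day, and do not treat a negative before Day 14 as a Day 14 negative. Section 10.3 plans a listing for plasma antibodies only, so add one for serum antibodies.
- Tables 14.2.2.1 and 14.2.2.2, Overall column: show a subject with no postdose sample as missing, and give the number assessed beside the number dosed.
- Section 8.4 keeps early-termination results out of the laboratory summaries, so confirm that exit thrombin time appears in the coagulation listing.

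**Cost.** Wording changes, up to 14 mL more blood per early terminator (within the 50 mL allowance under Table 3), and up to two antibody assays (plasma E-WE and serum wild-type thrombin), plus the check-in sample if either is positive.
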